#### 8.2 Statistical Methods

8.2.1 The reference (RRref) will be obtained by measuring respiration rate based on manual annotations of respiratory inspirations and expirations. Bias will be reported using the following equation and will be used for each site, subject, and for all data combined:

$$Bias = \frac{1}{n} \sum_{i=1}^{n} (RR_a - RR_{ref})$$

8.2.1.1 Optional analysis may be performed based on the available capnography data collected from subjects who could tolerate the device. The statistical formula for calculating bias for the capnography results will be similar to the above equation but with RRa replaced by respiratory rate from capnography (RRcap).

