#### 3 STUDY OBJECTIVES

The objective of this clinical investigational study is to compare the acoustic respiration rates (RRa) obtained using the INVSENSOR0004 sensor in the subjects up to 10 kg with the respiration rates determined by manual annotations (RRref), and when applicable with capnography respiration rate (RRcap).

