#### 4.2 Study Outcome and Measurement

Evaluation on the comparison of RRa measurements will be reported as a bias of between the acoustic respiration rate (RRa) parameter and the manual annotation (RRref).

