#### 8 STATISTICAL PLAN

8.1 Sample Size Determination

8.1.1 For equivalence study the sample size is given by  $N = \left(\frac{(z_{\alpha/2} + z_{\beta}) \cdot \sigma}{\delta}\right)^2$  where

 $z_{\alpha/2}$  is the standard normal distribution z-score with tail area  $\alpha/2$ 

 $z_{\beta}$  is the standard normal distribution z-score with tail area  $\beta$ 

 $\delta$  is the limit of equivalence

 $\sigma$  is the a-priori estimate of standard deviation (precision)

For Type I error rate or  $\alpha = 5\%$ ,  $z_{\alpha/2} = 1.96$ 

For Type II error rate or  $\beta = 20\%$  or power = 80%,  $z_{\beta} = 0.85$ 

 $\delta = 2.0 \text{ RPM}$ 

 $\sigma = 3.0 \text{ RPM}$ 

$$N = \left(\frac{(1.96+0.85)\cdot 3}{2}\right)^2 = 18$$

This study will use a minimum of 18 subjects with up to 100 subjects to account for possible events such as subject withdrawal, device deficiencies, and/or incomplete cases.

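### The study is sized for equivalence within 2.0 RPM, but only signed mean biases are planned: no interval, no comparison with the limit, and no measure of error size

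*Combined protocol and SAP*

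**What the plan says.** Section 8.1 opens its calculation with "For equivalence study the sample size is given by" and defines delta as the quantity that "is the limit of equivalence", set at 2.0 RPM. Sigma, a prior SD that the section also labels as precision, is 3.0 RPM. Alpha is 5% (z = 1.96) and power is 80% (z = 0.85). The result is N = 18, and "This study will use a minimum of 18 subjects with up to 100 subjects".

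Section 4.2 says the comparison "will be reported as a bias of between the acoustic respiration rate (RRa) parameter and the manual annotation". Section 8.2 gives one formula, the mean of RRa minus RRref, and states: "Bias will be reported using the following equation and will be used for each site, subject, and for all data combined". For the optional capnography analysis, "The statistical formula for calculating bias for the capnography results will be similar to the above equation".

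Neither 4.2 nor 8.2 contains a hypothesis, a confidence interval, an acceptance criterion or a measure of spread. The 2.0 RPM limit and the SD appear only in 8.1. Sections 3 and 4.1 speak only of comparing the rates.

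**The concern.** Two things are missing.

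1. **No decision rule.** A point estimate has no Type I error and no power. The alpha and power in 8.1 therefore describe a test that the plan never specifies. Nor does the plan settle whether equivalence is to be concluded or the study is descriptive. As it stands, whether the data meet the 2.0 RPM limit would be decided with an interval level, method and unit of analysis chosen after the results are known.

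2. **No measure of error size.** A signed mean lets positive and negative errors offset each other. Section 1.1 criticises existing monitors for low accuracy that leads to false alarms, and that depends on how far individual readings stray. The precision assumed in 8.1 is not among the planned results, so the assumption would never be compared with the data.

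**Working it through.** **The plan's own figure (inputs from 8.1).** N = ((1.96 + 0.85) × 3 / 2)² = 17.77, rounded up to 18. It reproduces.

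Section 8.1 does not say which SD sigma is, so both readings are worked through.

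**Reading A: sigma = 3.0 is the SD of subject-level differences**

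Interval half-width = t(n-1) × 3 / √n.

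| n | 95% half-width (RPM) | 90% half-width (RPM) |
|---|---|---|
| 18 | 2.110 × 3 / √18 = 1.49 | 1.740 × 3 / √18 = 1.23 |
| 38 | 2.026 × 3 / √38 = 0.99 | 0.82 |
| 100 | 1.984 × 3 / √100 = 0.60 | 0.50 |

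The smallest n with a 95% half-width of at most 1.0 RPM is 38.

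At n = 18 with a sample SD of 3, the largest observed bias whose interval stays inside ±2.0 RPM is:
- 95% interval: 2 - 1.49 = 0.51 RPM
- 90% interval: 2 - 1.23 = 0.77 RPM

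An observed bias of 1.0 RPM has a 95% interval of 1.0 ± 1.49, that is -0.49 to 2.49. The point estimate is inside the limit but the interval is not.

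**Power if the rule were that the whole t-interval lies within ±2.0 RPM**

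Power = P(|mean| + t × s / √n < 2), with the mean distributed as N(true bias, 9/n) and (n-1)s²/9 as chi-square on n-1 degrees of freedom. It was integrated over s. The plan gives no true bias, so the values below are assumptions.

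- n = 18, true bias 0: 52% (95% interval), 71% (90% interval). A simulation of 400,000 runs agrees.
- Smallest n for 80% power:

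| Assumed true bias (RPM) | 95% interval | 90% interval |
|---|---|---|
| 0 | 26 | 21 |
| 0.5 | 34 | 27 |
| 1.0 | 73 | 58 |

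**Reading B: sigma = 3.0 is the SD of single readings (normal errors, zero bias)**

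- P(|error| > 2) = 2 × (1 - Φ(2/3)) = 0.505, so about half of readings are off by more than 2 RPM.
- 95% limits of agreement = ±1.96 × 3 = ±5.9 RPM.

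**Cancellation within an infant (assumed SDs, normal errors, zero bias in every infant)**

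- Within-infant SD 1 RPM: P(|error| > 2) = 2 × (1 - Φ(2)) = 5%.
- Within-infant SD 5 RPM: P(|error| > 2) = 2 × (1 - Φ(0.4)) = 69%.

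In both cases every expected site, subject and overall bias is 0, so the results planned in 8.2 would not separate the two sensors.

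**The case against.** The strongest reply is that 8.1 already fixes the equivalence framing, the limit, alpha and z = 1.96, so that only a linking sentence is missing. Much of this is fair: the limit and alpha are set in advance. But alpha of 5% does not settle whether the interval is 95% or 90%, and nothing says how repeated readings within a subject are handled.

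A second reply is that the per-subject biases in 8.2 reveal spread. They do show spread between subjects, and a reader could derive an SD and an interval from them afterwards. They do not show error within an infant, and an interval built afterwards is not pre-specified.

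Third, the plan sets no criterion for individual readings, false alarms are background rather than an outcome, and the choice among spread measures is partly preference. That stands as far as it goes, which is why the fix leaves the choice of measure open. The argument from inside the plan is that 8.1 assumes a precision that is never reported.

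Finally, 18 is a floor. At 100 subjects, power under the interval rule is at least 91% for every true bias shown above. However, 8.1 justifies enrolment beyond 18 only by losses such as withdrawals, device deficiencies and incomplete cases, so the stated 80% rests on 18.

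The within-infant SDs and the true biases are illustrations. They show what the planned summaries could hide, not what this study will find.

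**Conclusion.** The concern holds and must be fixed. Followed exactly, the plan yields point estimates that cannot support the equivalence conclusion the study was sized for, and it gives no view of error size within an infant. The arithmetic behind N = 18 is correct on its own terms; the fault is that no planned analysis uses it.

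The size depends on what sigma means. As a subject-level SD, the unreported 95% uncertainty is ±1.49 RPM at n = 18, about three quarters of the 2.0 RPM limit (1.49 / 2.0 = 0.75), falling to ±0.60 at n = 100. As a per-reading SD with normal errors, a zero bias is compatible with about half of readings missing by more than 2 RPM. The power figures additionally assume independent, normally distributed subject-level differences and the interval rule described above.

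**What to change.** **If equivalence is intended**, revise 4.2, 8.1 and 8.2 as follows:

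- Report mean bias with a confidence interval that treats the subject as the unit: a t-interval on subject-level biases, or a method for the pooled bias that allows for repeated readings.
- Conclude equivalence only if the whole interval lies within ±2.0 RPM, at a level fixed in advance: 95% if z = 1.96 is taken literally, 90% if 5% per side is meant.
- Report the SD of the differences and 95% limits of agreement allowing for repeated readings, or the root-mean-square error.
- State in 8.1 which SD sigma = 3.0 is, and restate the power for this rule.

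**If the study is descriptive**, remove the equivalence, alpha and power wording from 8.1 and justify n by the precision of the bias, using the half-widths above if the subject-level SD is 3. Still report the interval and the error-size measure.

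**Cost.** Short text changes and further analysis of data already collected. On the equivalence route the sponsor accepts a criterion that can be failed and a less favourable power statement. The minimum of 18 need not rise if the power is restated. Keeping 80% requires the numbers of analysed subjects tabulated above, all within the existing ceiling of 100. The descriptive route adds no pass/fail criterion but gives up any equivalence conclusion.

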#### 1.1 Background and Rationale

Recording vital signs (pulse rate, respiratory rate, blood pressure and temperature) is the standard of care for all patients on the hospital ward. However, documentation of vital signs is often poor or inaccurate. Of the four vital signs, respiratory rate is particularly difficult to assess and often not recorded in the patient record. This is in spite of the fact that elevated respiratory rate is one of the best predictors of respiratory deterioration, cardiac arrest and admission to the intensive care unit (ICU).

[figure not shown]
A simple noninvasive device to continuously monitor respiratory rate is therefore highly desirable. However, existing automated methods have had limited success in broad adoption due to either low accuracy leading to too many false alarms or due to poor patient tolerance for continuous monitoring. These current methods include impedance pneumography (taken from standard ECG electrodes) and end-tidal carbon dioxide monitoring that utilizes a special nasal cannula to sample respiratory gases. The former suffers from low accuracy resulting in high false alarm rates . In addition, impedance pneumography is a measure of respiratory effort and is known not to detect obstructive apneas, a major requirement for continuous surveillance monitoring of at risk patients. Capnography (ETCO2) monitoring is commonly used in the operating room/anesthesia setting but is not well tolerated in other patient care areas due to patient wearability issues that have resulted in limited compliance.

These limitations led Masimo Corporation to develop the rainbow Acoustic Monitoring (RAM) system with Masimo's Signal Extraction Technology (SET®). RAM noninvasively and continuously monitors and measures the acoustic respiration rates (RRa) and waveforms using an adhesive sensor with an integrated acoustic transducer converting acoustical airflow patterns to respiration rates. The RRa has shown to be accurate and reliable in offering clinical facilitations in early detection of respiratory compromise and patient distress in comparison to capnography monitoring .

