#### 2.3 Risk/Benefits

**Benefits:** There will be no direct benefits to the enrolled subjects. Future benefits of continuous noninvasive respiration rate monitoring may aid clinicians to predict respiration deterioration in pediatric population in hospitals, hospital-type facilities, mobile, and home environments.

**Sensor risks:** As with all RAM sensors and pulse oximeter sensors there is risk of thermal burn and skin irritation, discomfort, and redness due to the sensor adhesive. The design includes safeguards, and this risk is believed to be low.

All patient-contacting materials, including the adhesive used in the design of the Masimo Rainbow sensors, have been subjected to biocompatibility tests per ISO 10993-1, ISO 10993-5, ISO 10993-10 and results demonstrate that the materials are non-toxic, non-irritating, and non-sensitizing. The sensors have been subjected to performance, mechanical, and electrical testing and results demonstrate that the sensors meet the requirements for safety and effectiveness for the intended use of the product. The modifications to the sensor are specifically designed so as not to introduce any new risks to the subject, and have been developed pursuant to the design control regulations per ISO 14971.

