#### **6 SUBJECT SELECTION AND WITHDRAWAL**

#### 6.1 Population Base

Subjects will be healthy and non-healthy subjects. Subjects will be recruited from diversified demographics (age, gender, ethnicity, skin tone, comorbidities, etc).

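### Bias is never reported by level of respiratory rate, so error that changes with rate can be diluted or cancel in the combined figure

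*Combined protocol and SAP*

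**What the plan says.** Section 1.1 builds the case for continuous monitoring on the statement that "elevated respiratory rate is one of the best predictors of respiratory deterioration". Section 2.3 describes a future benefit in similar terms: monitoring "may aid clinicians to predict respiration deterioration in pediatric population".

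The outcome in section 4.2 "will be reported as a bias of between the acoustic respiration rate (RRa) parameter and the manual annotation". Section 8.2.1 gives the formula, a mean of signed differences RRa − RRref, which "will be used for each site, subject, and for all data combined". These three levels are the only ones named.

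On who supplies the data, section 6.1 states that "Subjects will be healthy and non-healthy subjects" and asks for diversity in demographics and comorbidities. Section 6.2 selects by weight, by care setting (NICU, PICU or PACU) and by consent; section 6.3 excludes mainly on skin condition. Respiratory rate is not a criterion, a quota or a coverage target in any of them.

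Section 8.1 uses a single equivalence limit of 2.0 RPM and a single standard deviation of 3.0 RPM, neither linked to rate, and arrives at a minimum of 18 subjects with a ceiling of 100.

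**The concern.** A monitor that is accurate at ordinary rates may still read low when breathing is fast or high when it is slow. Section 1.1 gives elevated rates as the reason to want the device, so that is where its accuracy matters most. A mean signed difference over all readings weights each rate level by how often it happens to occur, and lets errors of opposite sign offset each other. The study could report a small combined bias while the error at high rates is large. It could also include few high-rate readings without the report showing it. A pooled measure of spread would not settle this either: it would show that some errors are large, but not at which rates.

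**Working it through.** **The plan's own figure.** Section 8.1: N = ((1.96 + 0.85) × 3 / 2)² = 4.215² = 17.77, rounded up to 18. This reproduces. The point here is not an arithmetic error.

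**Dilution.** Taking the combined figure as a mean over all paired readings, combined bias = Σ (share of readings at a rate level × bias at that level). The documents give no distribution of rates and no error by rate, so every share and error below is an assumption. With zero bias elsewhere:

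| Share at high rates | Error there | Combined bias |
|---|---|---|
| 5% | −10 RPM | 0.05 × (−10) = −0.5 RPM |
| 10% | −10 RPM | 0.10 × (−10) = −1.0 RPM |
| 5% | −15 RPM | 0.05 × (−15) = −0.75 RPM |
| 10% | −15 RPM | 0.10 × (−15) = −1.5 RPM |

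All four are smaller in size than 2.0 RPM. For the combined bias to reach 2.0 RPM, the error at high rates would have to be 2.0 / 0.10 = 20 RPM at a 10% share, or 2.0 / 0.05 = 40 RPM at a 5% share.

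**Cancellation.** With 10% of readings at −10 RPM, a bias of 0.10 × 10 / 0.90 = +1.1 RPM in the other 90% brings the combined figure to zero.

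**Bias per subject.** The same formula applies within one subject. If the rate is high throughout and the error is −15 RPM, that subject's bias is −15 RPM and is plain to see. If fast breathing fills 10% of the recording, it is 0.10 × (−15) = −1.5 RPM and looks unremarkable.

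**Spread implied by the illustration.** A share f with error b, and zero elsewhere, gives a standard deviation of |b| × √(f(1 − f)) before any other error: 10 × √0.0475 = 2.2, 10 × √0.09 = 3.0, 15 × √0.0475 = 3.3 and 15 × √0.09 = 4.5 RPM.

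**Coverage.** If a proportion p of eligible subjects show a high rate (assumed, subjects independent), the chance that 18 subjects include none is (1 − p)¹⁸: 70% at p = 2%, 40% at 5%, 15% at 10% and 2% at 20%. With 100 subjects it is 13% at 2% and 0.6% at 5%.

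**Precision by band.** With the plan's standard deviation of 3.0 RPM, taken here as between subjects, the approximate 95% half-width is 1.96 × 3 / √m. It is 1.4 RPM for m = 18, 2.4 RPM for m = 6 (18 subjects split evenly over three bands) and 2.9 RPM for m = 4.

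**The case against.** The best defence is that the study does what its objective asks. Section 3 asks for a comparison of RRa with RRref and sets no rate range; the remarks on elevated rate are background, and section 2.3 speaks of future benefits. This stands in part. The gap is between the rationale and the analysis, and the study does not fail its stated objective.

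Bias per subject is a real safeguard for a persistently high rate, and recruitment from NICU and PICU may well bring in varied rates. Both points stand as partial mitigation. Neither ties the result to rate, and nothing checks that the variety arrives.

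Most of the illustrated errors would also produce a spread at or above the planned 3.0 RPM, so a pooled spread statistic might raise an alarm. That is fair, although section 8.1 does not say whether 3.0 RPM is per reading or per subject, section 8.2 plans no spread statistic, and such a statistic would not locate the error.

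Three stronger readings are tempting, and the documents do not support them.

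- A reader might infer that the study promises to test apnea detection. Section 1.1 mentions apnea only as a criticism of impedance pneumography, which it calls "known not to detect obstructive apneas, a major requirement for continuous surveillance monitoring of at risk patients". The objective and the outcome do not claim it.
- A reader might infer that the sample is one of convenience, dominated by unremarkable breathing. The protocol does not say so. It plans diverse recruitment, includes two intensive-care settings and gives no distribution of rates.
- A reader might infer that the device would wrongly pass a 2.0 RPM test or earn an unrestricted claim. The 2.0 RPM limit is an input to sample sizing. Section 8.2 states no acceptance rule and draws no conclusion; it simply sets no bounds on one.

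**Conclusion.** The point holds as a gap in reporting. Section 8.2.1 cannot show whether RRa − RRref changes with rate, and no section sets or checks the range of RRref covered. Under assumed shares of 5% to 10% and assumed errors of 10 to 15 RPM with none elsewhere, the combined bias is −0.5 to −1.5 RPM. These figures show what the summary can conceal; they are not evidence that the sensor has such an error. Per-subject bias narrows the gap for subjects with a sustained high rate and leaves it open for short episodes and for a trend with rate. Recording lengths and breath-count details in section 7.2 are blanked and are not counted as omissions; section 8.2 shows no visible gap where an analysis by rate might have stood. This is a cheap improvement in what the study can conclude, not a defect that invalidates it.

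**What to change.** Add to section 8.2.1:

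- Report the bias and spread of RRa − RRref by level of RRref. Use either bands with cut-points fixed before RRa is compared with RRref, or a plot or regression of the difference on rate. In either case allow for repeated readings within a subject.
- Give the number of subjects and of paired readings in each band.
- Limit the accuracy statement to the range of RRref observed.

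The manual annotations that define RRref are already planned (sections 2.1 and 8.2.1), so this needs SAP wording and one table or figure, with no new subjects or procedures. It does not make high rates occur; it makes their absence visible.

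There are three costs. Estimates in sparse bands will be imprecise: with 4 subjects the half-width of 2.9 RPM exceeds the 2.0 RPM used for sizing. Grouping on RRref also creates some apparent trend of its own. If RRref carries annotation error independent of the error in RRa, the difference tends to look negative where RRref is high and positive where it is low, even with no true dependence on rate. Repeating the analysis against the mean of the two methods is a useful check, though it removes this effect fully only if the two error variances are similar. Lastly, the claim may be narrower than one made for all rates.

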#### 9 SAFETY AND ADVERSE EVENTS

#### 9.1 Definitions

The definitions for adverse event, adverse device effect, serious adverse event, serious adverse device effect, and unanticipated adverse device effect are provided below (ISO 14155:2011, 21 CFR 812.3(s)).

- Adverse Event (AE): an adverse event is any untoward medical occurrence in a subject which need not be related to the
  device under investigation.
- Adverse Device Effect (ADE): an adverse device effect is any untoward or unintended response to a medical device which may result from insufficiencies in the instructions for use or deployment of the device, or from use error.
- Serious Adverse Event (SAE): a serious adverse event is an adverse event that results in death, inpatient hospitalization, severe or permanent disability, a life threatening illness or injury, fetal distress, fetal death, a congenital abnormality, a birth defect, or medical or surgical intervention to prevent permanent impairment to body or structure.
- Serious Adverse Device Effect (SADE): a serious adverse device effect is an adverse device effect that results in death, inpatient hospitalization, severe or permanent disability or is life threatening.

<sup>1 Sample Size Calculations, Practical Methods for Engineer and Scientists, Paul Mathews ISBN 978-0-615-32461-6

• Unanticipated Adverse Device Effect (UADE): any serious adverse effect on health or safety or any life threatening problem or death cause by or associated with, a device, if the effect, problem, or death was not previously identified in nature, severity or degree of incidence in the investigational plan, or application (including a supplementary plan or application) or any other unanticipated serious problem associated with a device that related to the rights, safety or welfare of subjects. Refer to the Device Risk Analysis and Risk Assessment section for details on anticipated adverse device effects.

